4.5.1.2 Dose Delay Criteria for Nivolumab and/or Ipilimumab Therapy

Nivolumab and/or ipilimumab administration should be delayed for the following:

- Any Grade ≥ 2 non-skin, drug-related AE, with the following exception:
 - Grade 2 drug-related fatigue does not require a treatment delay.
- Grade 2 drug-related creatinine, AST, ALT and/or Total Bilirubin abnormalities
- Any Grade 3 skin, drug-related AE
- Any Grade 3 drug-related laboratory abnormality (excluding AST, ALT or Total Bilirubin), with the following exceptions for lymphopenia, and asymptomatic amylase or lipase abnormalities:
 - Grade 3 lymphopenia does not require dose delay
 - Any Grade ≥ 3 drug-related amylase or lipase abnormality that is not associated with symptoms or clinical manifestations of pancreatitis does not require dose delay.
- Any AE, laboratory abnormality, or intercurrent illness which, in the judgment of the investigator, warrants delaying the dose of study medication.

Subjects receiving ipilimumab in combination with nivolumab who have drug-related toxicities that meet the criteria for dose delay should have both drugs (ipilimumab and nivolumab) delayed until retreatment criteria are met (exceptions apply to the retreatment criteria after dose delay of ipilimumab and nivolumab for Grade ≥ 3 amylase and lipase abnormalities that are not associated

with symptoms or clinical manifestations of pancreatitis and that are attributed to ipilimumab and/or nivolumab).

Subjects who require delay of nivolumab and ipilimumab should be re-evaluated weekly or more frequently if clinically indicated and resume nivolumab and/or ipilimumab dosing when re-treatment criteria are met.

4.5.1.3 Dose Reductions for Nivolumab or Ipilimumab Therapy

There will be no dose reductions for nivolumab or ipilimumab.

4.5.1.4 Criteria for Resuming Treatment for Nivolumab or Ipilimumab

Subjects may resume treatment with study drug when the drug-related AE(s) resolve to Grade ≤ 1 or baseline value, with the following exceptions:

- Subjects may resume treatment in the presence of Grade 2 fatigue.
- Subjects who have not experienced a Grade 3 drug-related skin AE may resume treatment in the presence of Grade 2 skin toxicity.
- For subjects with Grade 2 AST, ALT, or total bilirubin elevations, dosing may resume when laboratory values return to baseline and management with corticosteroids, if needed, is complete.
- Subjects with combined Grade 2 AST/ALT AND total bilirubin values meeting discontinuation parameters (Section 4.5.1.5) should have treatment permanently discontinued.
- Drug-related pulmonary toxicity, diarrhea, or colitis must have resolved to baseline before treatment is resumed. Subjects with persistent Grade 1 pneumonitis after completion of a steroid taper over at least 1 month may be eligible for retreatment if discussed with and approved by BMS Medical Monitor.
- Subjects with drug-related endocrinopathies adequately controlled with only physiologic hormone replacement may resume treatment after consultation with the BMS Medical Monitor.
- Participants who received systemic corticosteroids for the management of any drug-related toxicity must be off corticosteroids or have tapered down to an equivalent dose of prednisone ≤ 10 mg/day.

If the criteria to resume treatment are met, the subject should restart treatment at the next scheduled timepoint per protocol. However, if the treatment is delayed past the scheduled timepoint per protocol, the scheduled study treatment administration will be delayed, but not skipped, until dosing resumes. In particular, this is to ensure that subjects will receive 4 administrations of combined nivolumab and ipilimumab treatment if toxicity allows.

If dose delay is necessary for subjects during Week 1 - 12, both nivolumab and ipilimumab must be delayed until treatment can resume. However, if a nivolumab-related infusion reaction prevents subsequent infusion of ipilimumab on the same day, the dose of ipilimumab should be replaced as soon as possible. In such instances, at least 19 days must elapse between the replacement dose of ipilimumab and the administration of the next dose of nivolumab combined with ipilimumab.

If treatment is delayed > 6 weeks, the subject must be permanently discontinued from study therapy, except as specified in Section 4.5.1.5.

Clinical Protocol BMS-936558

4.5.1.5 Criteria for Nivolumab and/or Ipilimumab Treatment Discontinuation

Treatment should be permanently discontinued for the following:

 Any Grade 2 drug-related uveitis, eye pain or blurred vision that does not respond to topical therapy and does not improve to Grade 1 severity within the re-treatment period OR requires systemic treatment

- Any Grade 3 non-skin, drug-related adverse event lasting > 7 days or recurs, with the following exceptions for laboratory abnormalities, diarrhea, colitis, neurologic toxicity, drug-related uveitis, pneumonitis, bronchospasm, neurologic toxicity, hypersensitivity reactions, infusion reactions, and endocrinopathies:
 - Grade 3 drug-related diarrhea, colitis, neurologic toxicity, myocarditis, uveitis, pneumonitis, bronchospasm, hypersensitivity reaction, or infusion reaction of any duration requires discontinuation
 - Grade 3 drug-related endocrinopathies adequately controlled with only physiologic hormone replacement do not require discontinuation. Grade ≥ 3 adrenal insufficiency requires discontinuation regardless of control with hormone replacement (note: Hospitalization for diagnostic workup of adrenal insufficiency without severe symptoms should not be considered a Grade 3 event)
 - Grade 3 drug-related laboratory abnormalities do not require treatment discontinuation except:
 - ◆ Grade 3 drug-related thrombocytopenia > 7 days or associated with bleeding requires discontinuation
 - Grade ≥ 3 drug-related AST, ALT or Total Bilirubin requires discontinuation*
 - ♦ Concurrent AST or ALT > 3 x ULN and total bilirubin > 2x ULN
- *In most cases of Grade 3 AST or ALT elevation, study drug(s) will be permanently discontinued. If the investigator determines a possible favorable benefit/risk ratio that warrants continuation of study drug(s), a discussion between the investigator and the BMS Medical Monitor/designee must occur.
- Any Grade 4 drug-related AE or laboratory abnormality (including but not limited to creatinine, AST, ALT, or total bilirubin), except for the following events which do not require discontinuation:
 - Grade 4 neutropenia \leq 7 days
 - Grade 4 lymphopenia or leukopenia
 - Isolated Grade 4 amylase or lipase abnormalities that are not associated with symptoms or clinical manifestations of pancreatitis.
 - Isolated Grade 4 electrolyte imbalances/abnormalities that are not associated with clinical sequelae and are corrected with supplementation/appropriate management within 72 hours of their onset
 - Grade 4 drug-related endocrinopathy AEs, such as hyper- or hypothyroidism, or glucose intolerance, which resolve or are adequately controlled with physiologic hormone replacement (corticosteroids, thyroid hormones) or glucose-controlling agents, respectively, may not require discontinuation after discussion with and approval from the BMS Medical Monitor.
- Any event that leads to delay in dosing lasting > 6 weeks from the previous dose requires discontinuation, with the following exceptions:

Revised Protocol No.: 09 Date: 16-Sep-2019 CA209649

nivolumab

- Dosing delays to allow for prolonged steroid tapers to manage drug-related AEs are allowed.
- Dosing delays lasting > 6 weeks from the previous dose that occur for non-drug-related reasons may be allowed if approved by the BMS medical monitor.
- Any AE, laboratory abnormality, or intercurrent illness which, in the judgment of the Investigator, presents a substantial clinical risk to the subject with continued nivolumab dosing.

Prior to re-initiating treatment in a subject with a dosing delay lasting > 6 weeks from the previous dose, the BMS medical monitor must be consulted. Tumor assessments should continue as per protocol even if dosing is delayed.

The assessment for discontinuation of ipilimumab should be made separately from the assessment made for discontinuation of nivolumab. Although there is overlap among the discontinuation criteria, if discontinuation criteria are met for ipilimumab but not for nivolumab, treatment with nivolumab may continue if ipilimumab is discontinued.

If a subject meets the criteria for discontinuation of ipilimumab but not nivolumab, treatment with nivolumab may not resume until the AE has fully resolved and the subject has discontinued steroids, if they were required for treatment of the AE. The relationship to ipilimumab should be well documented in the source documents. Nivolumab should be resumed at 240 mg every 2 weeks.

If a subject in any of the nivolumab/ipilimumab combination arms meets criteria for discontinuation and investigator is unable to determine whether the event is related to both or one study drug, the subject should discontinue both nivolumab and ipilimumab and be taken off the treatment phase of the study.

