APPENDIX 1 MANAGEMENT ALGORITHMS

These general guidelines constitute guidance to the Investigator and may be supplemented by discussions with the Medical Monitor representing the Sponsor. The guidance applies to all immuno-oncology agents and regimens.

A general principle is that differential diagnoses should be diligently evaluated according to standard medical practice. Non-inflammatory etiologies should be considered and appropriately treated.

[figure not shown]
Corticosteroids are a primary therapy for immuno-oncology drug-related adverse events. The oral equivalent of the recommended IV doses may be considered for ambulatory patients with low-grade toxicity. The lower bioavailability of oral corticosteroids should be taken into account when switching to the equivalent dose of oral corticosteroids.

Consultation with a medical or surgical specialist, especially prior to an invasive diagnostic or therapeutic procedure, is recommended.

The frequency and severity of the related adverse events covered by these algorithms will depend on the immuno-oncology agent or regimen being used.

GI Adverse Event Management Algorithm

Rule out non-inflammatory causes. If non-inflammatory cause is identified, treat accordingly and continue I-O therapy. Opiates/narcotics may mask symptoms of perforation. Infliximab should not be used in cases of perforation or sepsis.

[figure not shown]

Patients on IV steroids may be switched to an equivalent dose of oral corticosteroids (e.g. prednisone) at start of tapering or earlier, once sustained clinical improvement is observed. Lower bioavailability of oral corticosteroids should be taken into account when switching to the equivalent dose of oral corticosteroids.

27-Jun-2019

Renal Adverse Event Management Algorithm

Rule out non-inflammatory causes. If non-inflammatory cause, treat accordingly and continue I-O therapy.

[figure not shown]

Patients on IV steroids may be switched to an equivalent dose of oral corticosteroids (e.g. prednisone) at start of tapering or earlier, once sustained clinical improvement is observed. Lower bioavailability of oral corticosteroids should be taken into account when switching to the equivalent dose of oral corticosteroids.

27-Jun-2019

Pulmonary Adverse Event Management Algorithm

Rule out non-inflammatory causes. If non-inflammatory cause, treat accordingly and continue I-O therapy. Evaluate with imaging and pulmonary consultation.

[figure not shown]

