Patients on IV steroids may be switched to an equivalent dose of oral corticosteroids (e.g. prednisone) at start of tapering or earlier, once sustained clinical improvement is observed. Lower bioavailability of oral corticosteroids should be taken into account when switching to the equivalent dose of oral corticosteroids

27-Jun-2019

Hepatic Adverse Event Management Algorithm

Rule out non-inflammatory causes. If non-inflammatory cause, treat accordingly and continue I-O therapy. Consider imaging for obstruction.

[figure not shown]
Patients on IV steroids may be switched to an equivalent dose of oral corticosteroids (e.g. prednisone) at start of tapering or earlier, once sustained clinical improvement is observed. Lower bioavailability of oral corticosteroids should be taken into account when switching to the equivalent dose of oral corticosteroids.

27-Jun-2019

^{*}The recommended starting dose for grade 4 hepatitis is 2 mg/kg/day methylprednisolone IV.

Endocrinopathy Adverse Event Management Algorithm

Rule out non-inflammatory causes. If non-inflammatory cause, treat accordingly and continue I-O therapy. Consider visual field testing, endocrinology consultation, and imaging.

[figure not shown]

Patients on IV steroids may be switched to an equivalent dose of oral corticosteroids (e.g. prednisone) at start of tapering or earlier, once sustained clinical improvement is observed. Lower bioavailability of oral corticosteroids should be taken into account when switching to the equivalent dose of oral corticosteroids.

27-Jun-2019

Skin Adverse Event Management Algorithm

Rule out non-inflammatory causes. If non-inflammatory cause, treat accordingly and continue I-O therapy.

Patients on IV steroids may be switched to an equivalent dose of oral corticosteroids (e.g. prednisone) at start of tapering or earlier, once sustained clinical improvement is observed. Lower bioavailability of oral corticosteroids should be taken into account when switching to the equivalent dose of oral corticosteroids.

[figure not shown]
^If SJS/TEN is suspected, withhold I-O therapy and refer patient for specialized care for assessment and treatment. If SJS or TEN is diagnosed, permanently discontinue I-O therapy.

27-Jun-2019

^{*}Refer to NCI CTCAE v4 for term-specific grading criteria.

Neurological Adverse Event Management Algorithm

[figure not shown]
Rule out non-inflammatory causes. If non-inflammatory cause, treat accordingly and continue I-O therapy.

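### The binding nivolumab/ipilimumab criteria allow conditional re-dosing after drug-related SJS or TEN recorded below Grade 4, whereas Appendix 1 requires a permanent stop on diagnosis.

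*Protocol*

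**What the plan says.** All the relevant text is in Revised Protocol 09.

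- **Section 3.5** lists the reasons for which a subject must stop. For toxicity it cites Sections 4.5.1.5 and 4.7. It does not cite Appendix 1.
- **Section 4.5.1.5** requires permanent discontinuation for "Any Grade 3 non-skin, drug-related adverse event lasting > 7 days or recurs", with listed exceptions, and for any Grade 4 drug-related event, with exceptions that include no skin event. SJS and TEN are not named.
- **Section 4.5.1.2** lists "Any Grade 3 skin, drug-related AE" as a reason to delay. Its Grade 2 rule applies to non-skin events.
- **Section 4.5.1.4** governs resumption: "Subjects may resume treatment with study drug when the drug-related AE(s) resolve to Grade ≤ 1 or baseline value". Subjects given systemic steroids for the toxicity "must be off corticosteroids or have tapered down to an equivalent dose of prednisone ≤ 10 mg/day". When the criteria are met, the section tells the site to restart at the next scheduled time point. None of its exceptions concerns SJS or TEN.
- **Appendix 1**, skin algorithm footnote: withhold immunotherapy if SJS/TEN is suspected, and "If SJS or TEN is diagnosed, permanently discontinue I-O therapy". No grade is attached. On its own status the appendix says: "These general guidelines constitute guidance to the Investigator and may be supplemented by discussions with the Medical Monitor representing the Sponsor".
- **Section 4.5.1.7** introduces the algorithms as help for investigators and points to Appendix 1. Nothing says which text governs where they differ.

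**The concern.** Two instructions in force in the same protocol lead to different actions for the same event. Once a drug-related SJS or TEN case recorded below Grade 4 has resolved, the numbered sections permit, and on their wording direct, a restart. The appendix forbids it. The text with mandatory force is the weaker one.

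The stake is patient safety. SJS/TEN can be fatal, and a site working from the numbered criteria alone could re-expose a subject to nivolumab after a diagnosed case. No estimand, test or event count is involved.

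**Working it through.** **1. Rule trace for drug-related SJS/TEN handled as a skin event**

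| Recorded grade | Sections 4.5.1.2, 4.5.1.4, 4.5.1.5 | Appendix 1 footnote | Agree? |
|---|---|---|---|
| 4 | Permanent stop | Permanent stop | Yes |
| 3 | Delay; resume at Grade 1 or baseline if the steroid condition is met | Permanent stop | No |
| 2 | No skin-specific delay; resumption allowed if there was no Grade 3 skin event | Permanent stop | No |

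The Grade 2 and 3 rows matter only if such gradings can occur. The appendix says "Refer to NCI CTCAE v4 for term-specific grading criteria", and that source is not in the documents, so this cannot be settled here.

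**2. Other provisions that could close the gap**

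- *Six-week limit.* "If treatment is delayed > 6 weeks, the subject must be permanently discontinued from study therapy, except as specified in Section 4.5.1.5". Section 4.5.1.5 counts the six weeks from the previous dose and exempts prolonged steroid tapers. The medical monitor must be consulted before re-starting, but only after a delay beyond that limit.
- *Hypersensitivity.* A Grade 3 hypersensitivity reaction is a permanent stop, but only if the site classes the event that way.
- *Investigator judgment.* Sections 3.5, 4.5.1.2 and 4.5.1.5 let the investigator stop or delay. These are discretionary.
- *Section 4.7.* Its stop for severe mucocutaneous reactions concerns capecitabine or leucovorin.
- *Section 4.5.2.2.* It sends management of nivolumab-related events in the chemotherapy combination arm to 4.5.1.7, and so to Appendix 1. The same section sends stopping to 4.5.1.5 and resuming to 4.5.1.4.

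None of these is an unconditional stop on diagnosis.

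**3. Subjects still exposed at 16-Sep-2019**

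The documents do not give this number, so it is modelled.

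*Randomized* (SAP Table 5.1-1):

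- Nivolumab plus chemotherapy: 1098/3 + 468/2 + 382/2 = 366 + 234 + 191 = 791.
- Nivolumab plus ipilimumab: 83/2 + 1098/3 = 41.5 + 366 = 407.5.

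*Assumptions.* Treatment lasts until a PFS event and ends at 24 months. Accrual is even within 27-Mar-2017 to 05-Jun-2018, 05-Jun-2018 to 15-Nov-2018, and 15-Nov-2018 to a date between 1 and 31 May 2019. One month is 30.4375 days.

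*Monthly hazards* (Protocol Table 8.1.4-1) over 0–3, 3–6, 6–10 and >10 months:

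- Chemotherapy: 0.09, 0.17, 0.20, 0.13.
- Combination, 3-month delay: 0.09, 0.17×0.56, 0.20×0.56, 0.13×0.56.
- Combination, 6-month delay: 0.09, 0.17, 0.20×0.56, 0.13×0.56.

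*Remaining* = number randomized in each accrual period × mean of exp(−cumulative hazard) over that period's follow-up times, set to zero beyond 24 months.

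| Arm and hazards | By accrual period | Total |
|---|---|---|
| Nivolumab + chemotherapy, 3-month delay | 40.7 + 70.9 + (96.1 to 101.6) | 207.7 to about 213.1 |
| Nivolumab + chemotherapy, 6-month delay | 32.5 + 56.7 + (78.2 to 84.9) | 167.4 to 174.1 |
| Nivolumab + ipilimumab, chemotherapy hazards | first period only | 13.6 |
| Nivolumab + ipilimumab, 6-month-delay hazards | first period only | 32.5 |
| Nivolumab + ipilimumab, 3-month-delay hazards | first period only | 40.7 |

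The documents give no PFS model for nivolumab plus ipilimumab, so the other arms' hazards bracket it. The 41.5 randomized before 27-Mar-2017 are past the 24-month cap.

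Total: 167.4 + 13.6 = 181.0, to 213.1 + 40.7 = 253.8.

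**4. Expected events below Grade 4**

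The documents give neither an SJS/TEN rate nor a grade split. The assumed ranges are 0.1% to 0.5% of subjects, with 10% to 50% of cases below Grade 4.

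- Low: 181.0 × 0.001 × 0.10 = 0.018.
- High: 253.8 × 0.005 × 0.50 = 0.63.
- If treatment beyond progression doubled the number still treated: 0.036 to 1.27.

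**5. Ipilimumab**

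From 05-Jun-2018 to 16-Sep-2019 is 468 days, or 468/7 = 66.9 weeks. The fourth and last ipilimumab dose is due at Week 10 (Section 4.5.1.1), so that course is over for essentially everyone.

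**The case against.** The best counter-argument is that the protocol already contains the right rule. Appendix 1 is part of the protocol, its SJS/TEN sentence is specific and unqualified, and a specific instruction would ordinarily be read over a general one. In the nivolumab-plus-chemotherapy arm, Section 4.5.2.2 leads to it, and that arm holds about 80% (167.4/208.1) to 94% (213.1/226.7) of those still on nivolumab. Re-dosing would also need an investigator who has diagnosed SJS/TEN to set aside the appendix and judge that neither discretionary stop applies.

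This makes re-dosing unlikely, but it does not reconcile the texts. The appendix calls itself guidance, Section 3.5 gives mandatory force to 4.5.1.5, and Section 4.5.2.2 sends the same arm to 4.5.1.4 and 4.5.1.5 for restarting and stopping.

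These further points stand and limit the finding:

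- A recorded grade below 4 is not shown to be possible for either term.
- Because 4.5.1.5 counts six weeks from the previous dose, an event just before the next dose leaves only 42 − 21 = 21 days on three-weekly dosing, or 42 − 28 = 14 days on four-weekly dosing, before the limit applies.
- The expected count includes every case below Grade 4, not just those that resolve, meet the steroid condition and are re-dosed, so it overstates re-dosing.
- The exposure model applies hazard ratios specified for CPS ≥ 5 subjects to everyone and ignores stops for toxicity.
- The skin algorithm figure is not shown, so the comparison rests on its printed footnotes.

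**Conclusion.** The concern holds as a minor safety inconsistency. For drug-related SJS or TEN recorded below Grade 4, the binding sections permit conditional re-dosing that the sponsor's own appendix rules out. A case that resolves inside the six-week limit, or later under the steroid-taper exception, can meet every numbered condition for a restart.

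Probably fewer than one subject would be affected, and ipilimumab re-dosing is essentially moot. Confidence is medium, because the count rests on assumed incidence, grade split and time on treatment, and because CTCAE v4 is not available to confirm the grading.

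**What to change.** Make three short insertions at the next amendment:

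- **4.5.1.5:** add diagnosed SJS or TEN, regardless of grade, to the permanent discontinuation list. The list already has event-specific stops such as myocarditis and pneumonitis, so the line fits.
- **4.5.1.2:** add suspected SJS/TEN to the reasons for delay.
- **4.5.1.4:** exclude diagnosed SJS/TEN from resumption.

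This carries the Appendix 1 rule into the sections that bind. It costs a few words of protocol text and needs no new data or change to any analysis.

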4.5.1.6 Treatment Beyond Disease Progression

Accumulating evidence indicates a minority of subjects treated with immunotherapy may derive clinical benefit despite initial evidence of PD. ⁸⁹

Subjects treated with nivolumab alone or in combination with ipilimumab or chemotherapy will be permitted to continue their treatment beyond initial RECIST 1.1-defined PD, assessed by the investigator, up to a maximum of 24 months from date of first dose, as long as they meet the following criteria:

- Investigator-assessed clinical benefit.
- Tolerance of study drug
- Stable performance status
- Treatment beyond progression will not delay an imminent intervention to prevent serious complications of disease progression (eg, CNS metastases)
- Subject provides written informed consent prior to receiving additional nivolumab treatment (alone or in combination with ipilimumab or chemotherapy). All other elements of the main consent including description of reasonably foreseeable risks or discomforts, or other alternative treatment options will still apply.

A radiographic assessment/scan should be performed within 6 weeks of initial investigator-assessed progression to determine whether there has been a decrease in the tumor size or continued PD. The assessment of clinical benefit should be balanced by clinical judgment as to whether the subject is clinically deteriorating and unlikely to receive any benefit from continued treatment with nivolumab plus ipilimumab or nivolumab.

If the investigator feels that the subject treated with nivolumab (alone or in combination with ipilimumab or chemotherapy) continues to achieve clinical benefit by continuing treatment, the subject should remain on the trial and continue to receive monitoring according to Table 5.1-2.

For the subjects who continue treatment beyond progression, further progression is defined as an additional 10% increase in tumor burden with a minimum 5 mm absolute increase from time of initial PD. This includes an increase in the sum of diameters of all target lesions and/ or the diameters of new measurable lesions compared to the time of initial PD. Nivolumab treatment (alone or in combination with ipilimumab or chemotherapy) should be discontinued permanently upon documentation of further progression.

New lesions are considered measureable at the time of initial progression if the longest diameter is at least 10 mm (except for pathological lymph nodes which must have a short axis of at least 15 mm). Any new lesion considered non-measureable at the time of initial progression may become measureable and therefore included in the tumor burden if the longest diameter increases to at least 10 mm (except for pathological lymph nodes which must have a short axis of at least 15 mm). In situations where the relative increase in total tumor burden by 10% is solely due to inclusion of new lesions which become measurable, these new lesions must demonstrate an absolute increase of at least 5 mm.

